5.2.2.2. Right censored Data

-NA-

5.2.2.3. Visit-specific censored Data

-NA-

5.3. Important protocol deviation not leading to elimination from per-protocol analysis set

Protocol Deviations were reviewed by the study team as the new process is not applicable for this study.

6. STATISTICAL ANALYSES

Note that standard data derivation rule and stat methods are described in annex 1 and will not be repeated below. All Confidence Interval (CI) will be two-sided 95% CI.

6.1. Demography

6.1.1. Analysis of demographics/baseline characteristics planned in the protocol

- The demographic characteristics (age in years at challenge dose, gender, geographic ancestry, height, weight and BMI) at Visit 1, cohort description and withdrawal status will be summarised using descriptive statistics. The same analysis will be performed stratified by age. The age stratification will be 40-50 and 51-60 years.
- Mean, median and standard deviation will be provided for continuous variables such as age.
- Frequency tables will be generated for categorical variables such as gender, race and centre

6.1.2. Additional considerations

All demography summaries will be generated for the TVC. The summary of age, height, weight, race and sex will also be provided for the ATP cohort. Summary of important protocol deviations not leading to elimination will be provided for the ATP cohort.

6.2. Exposure

6.2.1. Analysis of exposure planned in the protocol

-NA-

6.2.2. Additional considerations

The number of doses administered will be tabulated.

6.3. Immunogenicity

6.3.1. Analysis of immunogenicity planned in the protocol

The primary analysis on the response to the challenge dose will be performed on the ATP cohort for analysis of immunogenicity. If the percentage of subjects excluded from the ATP cohort for immunogenicity is more than 5%, a second analysis based on the TVC will be performed to complement the ATP analysis of immunogenicity. The immunogenicity analysis based on the TVC will include subjects for whom immunogenicity data are available. All the immunogenicity analysis will be performed as a whole group and by age stratification. The age stratification will be 40-50 years and 51-60 years.

The following analyses will be performed:

- The percentage of subjects with anti-HBs antibody concentrations ≥ 6.2 mIU/ml, ≥ 10 mIU/ml, ≥ 100 mIU/ml, ≥ 1000 mIU/ml with exact 95% CIs will be calculated at the pre-challenge dose time-point, Day 7 and Day 30 post-challenge dose time-points.
- The percentage of subjects who mount an anamnestic response to the challenge dose, one month after vaccination, will be tabulated with exact 95% CI as a whole and according to their seroprotection status at pre-challenge time-point (anti-HBs antibody concentrations \leq or ≥ 10 mIU/ml).
- GMCs with 95% CI will be calculated for anti-HBs antibodies at the pre-challenge dose time-point, Day 7 and Day 30 post-challenge dose time-points.
- The distribution of anti-HBs antibody concentrations will be displayed using reverse cumulative distribution curve (RCC) at the pre-challenge dose time-point and Day 30 post-challenge dose time-point.
- Relationship between pre-challenge dose time-point and Day 30 post-challenge dose time-point results will be presented by regression line graph.
- CMI responses in terms of frequency of HBs-specific CD4⁺ T-lymphocytes and frequency of HBs-specific memory B cells at Day 0, Day 7 and Day 30 (for subjects who received a challenge dose) will be evaluated.
- The percentage of subjects with anti-HBs concentrations ≥ 6.2 mIU/ml, ≥ 10 mIU/ml and ≥ 100 mIU/ml (with 95% CI) at the Day 7 and Day 30 post-challenge dose time-points will be tabulated in relation to their pre-challenge dose status (overall, < 10 mIU/ml and ≥ 10 mIU/ml).
- The percentage of subjects (with 95% CI) who mount an anamnestic response will be calculated and in relation to their pre-challenge dose status (< 10 mIU/ml and ≥ 10 mIU/ml)

Exploratory Analysis:

- Correlation between the anti-HBs specific T and memory B cells (frequency of cytokine-positive CD4⁺ or T-lymphocytes and frequency of memory B cells) with the amplitude of anamnestic response one month after the challenge dose will be analysed by Pearson's correlation coefficient.
- Further logistic regression modelling will be used to assess the impact of prognosis factors like age, gender, geographic ancestry, BMI and pre-vaccination status (seroprotected or not) on the seroprotection rate after the challenge dose. Actual age and BMI at the time of screening will be considered in the model

6.3.2. Additional considerations

-NA-

6.4. Analysis of safety

6.4.1. Analysis of safety planned in the protocol

The primary analysis will be performed on the TVC.

- The percentage of subjects who reported at least one local AE (solicited and unsolicited), with at least one general AE (solicited and unsolicited) and with any AE during the 4-day (Days 0-3) follow-up period after the vaccination will be tabulated with exact 95% CI. The same calculations will be performed for any Grade 3 (solicited or unsolicited) symptoms and any symptoms requiring medical attention.
- The percentage of subjects reporting each individual solicited symptom during the 4-day (Days 0-3) follow-up period with exact 95% CI, by type of AE; by severity (any Grade, Grade 3 only); by relationship to vaccination (any relationship, related only) will be tabulated.
- The occurrence of fever will be tabulated per 0.5°C cumulative increments as well as the occurrence of Grade 3 fever (> 39.0 °C axillary temperature) with causal relationship to vaccination.
- The percentage of subjects reporting at least one report of unsolicited AE classified by the Medical Dictionary for Regulatory Activities (MedDRA) and reported within the 31-day (Days 0-30) follow-up period after vaccination will be tabulated with exact 95% CI. The same tabulation will be performed for Grade 3 unsolicited AEs and for unsolicited AEs with a causal relationship to vaccination.
- SAEs during the entire study period and withdrawals due to AEs and SAEs reported during the 31-day follow-up period after the challenge dose will be described in detail.

6.4.2. Additional considerations

6.4.2.1. Combined Solicited and Unsolicited Adverse Events

For clinicaltrial.gov and EudraCT posting purposes, a summary of combined solicited and unsolicited non-serious adverse events will be produced by System Organ Class and preferred terms and according to occurrence of each event.

A summary of subjects with all combined solicited (regardless of their duration) and unsolicited adverse events will be provided. Solicited adverse events will be coded by MedDRA as per the following codes

| Solicited symptom | Lower level term code | Corresponding Lower level term decode |
|-------------------|-----------------------|---------------------------------------|
| PA | 10022086 | Injection site pain |
| RE | 10022098 | Redness at injection site |
| SW | 10053425 | Swelling at injection site |
| FA | 10016256 | Fatigue |
| TE | 10016558 | Fever |
| GI | 10017944 | Gastrointestinal disorder |
| HE | 10019211 | Headache |

7. ANALYSIS INTERPRETATION

All analyses are descriptive.

8. CONDUCT OF ANALYSES

8.1. Sequence of analyses

| Description | Analysis ID | Disclosure Purpose (CTRS=public posting, SR=study report, internal) | Dry run review needed (Y/N) | Study Headline Summary (SHS) requiring expedited communication to upper management (Yes/No) | Reference for TFL |
|---------------------|-------------|---|-----------------------------|---|----------------------------------|
| Analysis of epoch 1 | E1_01 | SR | Yes | Yes | TFL TOC first version - All TFLs |

8.2. Statistical considerations for interim analyses

No interim analysis planned for this study

9. CHANGES FROM PLANNED ANALYSES

-NA-

10. LIST OF FINAL REPORT TABLES, LISTINGS AND FIGURES

The TFL TOC provides the list of tables/listings and figures needed for the study report. It also identifies the tables eligible for each analyses and their role (synopsis, in-text, post-text, SHS, CTRS,). Note that all TFL aimed to be included as post-text are noted as post-text even if these are tabulation of individual data such as listing of SAE. The post-text material contain all source material for the study report and accordingly a post-text table may be redundant with an in-text table.

The following group names will be used in the TFLs, to be in line with the T-domains:

| Group order in tables | Group label in tables | Group definition for footnote | Pooled Groups label in tables | Pooled definition for footnote |
|-----------------------|-----------------------|-------------------------------------|-------------------------------|--------------------------------|
| 1 | HBV Group | HBV Engerix-B challenge dose | HBV Group | HBV Group |

The following sub-group names will be used in the TFLs

| Sub-group order in tables | Sub-group label in tables | Sub-group definition for footnote |
|---------------------------|---------------------------|-----------------------------------|
| 1 | 40-50 Y | 40-50 years old subjects |
| 2 | 51-60 Y | 51-60 years old subjects |

11. ANNEX 1 STANDARD DATA DERIVATION RULE AND STATISTICAL METHODS

11.1. Statistical Method References

The exact two-sided 95% CIs for a proportion within a group will be the Clopper-Pearson exact CI [Clopper CJ, Pearson ES. The use of confidence or fiducial limits illustrated in the case of binomial. *Biometrika*. 1934;26:404-413].

11.2. Standard data derivation

11.2.1. Date derivation

- SAS date derived from a character date: in case day is missing, 15 is used. In case day & month are missing, 30June is used.
- Onset day for an event (ae, medication, vaccination...): the onset day is the number of days between the last study vaccination & the onset/start date of the event. This is 0 for an event starting on the same day as a vaccination. See SAS date derived in case the start date of the event is incomplete.

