11.2.2. Dose number

- The study dose number is defined in reference to the number of study visits at which vaccination occurred. Specifically in this study, dose 1 refers to all vaccines administered at the first vaccination visit.
- Relative dose: the relative dose for an event (AE, medication, vaccination) is the most recent study dose given before an event. In case the event takes place on the day a study dose is given, the related dose will be that of the study dose, even if the event actually took place before vaccination. For instance, if an adverse event begins on the day of the study vaccination but prior to administration of the vaccine, it will be assigned to this dose.
- The number of doses for a product is the number of time the product was administered to a subject.

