11.2.5. Safety/Reactogenicity

- For the analyses of solicited symptoms, missing or non-evaluable measurements will not be replaced. Therefore, the analyses of the solicited symptoms based on the TVC will include only subjects with documented safety data (i.e. symptom screen completed).
- For the analyses of unsolicited adverse events/concomitant medication, all vaccinated subjects will be considered and subjects who did not report an event will be considered as subjects without an event.
- The maximum intensity of local injection site redness/swelling will be scored at GSK Biologicals as follows:

| | | |
|---|---|----------------------|
| 0 | : | Absent |
| 1 | : | ≤ 20 mm |
| 2 | : | >20 and ≤ 50 mm |
| 3 | : | > 50 mm |

- The maximum intensity of fever will be scored at GSK Biologicals as follows:

| Axillary | | |
|----------|---|-----------------------------------|
| 0 | : | < 37.5°C |
| 1 | : | ≥ 37.5 °C and ≤ 38.0 °C |
| 2 | : | > 38.0°C and ≤ 39.0 °C |
| 3 | : | > 39.0°C |

Note that for all tables described in this section, the way the percentage of subjects will be derived will depend on the event analysed (see table below for details). As a result, the N value may differ from one table to another.

| Event | N used for deriving % per subject for Vaccination phase | N used for deriving % per dose for Vaccination phase |
|---------------------------|--|--|
| Solicited general symptom | All subjects with at least one solicited general symptom documented as either present or absent (i.e., symptom screen completed) | All study visits with study vaccine administered and with at least one solicited general symptom documented as either present or absent (i.e., symptom screen completed) |
| Solicited local symptom | All subjects with at least one solicited local symptom documented as either present or absent (i.e., symptom screen completed) | All study visits with study vaccine administered and with at least one solicited local symptom documented as either present or absent (i.e., symptom screen completed) |
| Unsolicited symptom | All subjects with study vaccine administered | All study visits with study vaccine administered |
| Concomitant medication | All subjects with study vaccine administered | All study visits with study vaccine administered |

11.2.6. Number of decimals displayed:

The following decimal description from the decision rules will be used for the demography, immunogenicity and safety/reactogenicity.

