| | Related | | | | |
| | >39.0 Related | | | | |
| | Medical advice | | | | |

HBV : Engerix-B challenge dose

N = number of subjects with documented dose

n/% = number/percentage of subjects reporting the symptom at least once

95%CI = Exact 95% confidence interval; LL = lower limit, UL = upper limit

Template 26 Percentage of subjects reporting the occurrence of unsolicited symptoms classified by MedDRA Primary System Organ Class and Preferred Term within the 31-day (Days 0-30) post-vaccination period (Total Vaccinated Cohort)

| Primary System Organ Class (CODE) | Preferred Term (CODE) | HBV group N =XXX | | | |
|---|--------------------------------|---------------------|--|--|--|
| | | 95% CI | | | |
| At least one symptom | | | | | |
| Blood and lymphatic system disorders (10005329) | Anaemia (10002034) | | | | |
| | Hypochromic anaemia (10020969) | | | | |
| | Thrombocytopenia (10043554) | | | | |
| Immune system disorders (10021428) | Milk allergy (10027633) | | | | |
| Infections and infestations (10021881) | Bronchiolitis (10006448) | | | | |
| | Bronchitis (10006451) | | | | |
| | Gastroenteritis (10017888) | | | | |
| | Rash (10037844) | | | | |

HBV : Engerix-B challenge dose

At least one symptom = at least one symptom experienced (regardless of the MedDRA Preferred Term)

N = number of subjects with at least one administered dose

n/% = number/percentage of subjects reporting the symptom at least once

95% CI= exact 95% confidence interval; LL = Lower Limit, UL = Upper Limit

Template 27 Incidence of concomitant medication during the 4-day (Days 0-3) post-vaccination period (Total vaccinated cohort)

| | HBV group | | | 95% CI | |
|--------------------------|-----------|---|---|--------|----|
| | N | n | % | LL | UL |
| | | | | | |
| Any | | | | | |
| Any antipyretic | | | | | |
| Prophylactic antipyretic | | | | | |

HBV : Engerix-B challenge dose

95% CI = exact 95% confidence interval, LL = Lower Limit, UL = Upper Limit

Template 28 Number (%) of subjects reporting serious adverse events during the whole study period including number of events reported (Total vaccinated cohort)

| Type of Event | Primary System Organ Class | Preferred Term (CODE) | HBV group N = | | |
|-------------------|----------------------------|-----------------------|------------------|---|---|
| | | | n* | n | % |
| SAE | At least one symptom | | | | |
| | <each SOC> | <each PT term> | | | |
| Related SAE | At least one symptom | | | | |

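### The SAP's partial-date rule takes no account of the vaccination date, so an unsolicited adverse event with a missing onset day can fall outside Days 0-30

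*SAP*

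**What the plan says.** SAP 11.2.1 gives one rule for incomplete dates: "in case day is missing, 15 is used. In case day & month are missing, 30June is used". The 30 June value applies only when day and month are both unknown.

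The same section defines onset day: "the onset day is the number of days between the last study vaccination & the onset/start date of the event". It then sends incomplete event dates to the imputation rule: "See SAS date derived in case the start date of the event is incomplete". The imputed date therefore feeds onset day directly.

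Three other provisions determine what follows:

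- SAP 6.4.1 limits the unsolicited event table to events "reported within the 31-day (Days 0-30) follow-up period after vaccination will be tabulated with exact 95% CI". The combined table of solicited and unsolicited events covers a shorter window, "during the 4-day (Days 0-3) follow-up period after the vaccination will be tabulated with exact 95% CI". Template 26 repeats the 31-day limit.
- SAP 11.2.2 ties an event to a dose: "the relative dose for an event (AE, medication, vaccination) is the most recent study dose given before an event".
- SAP 11.2.5 keeps all vaccinated subjects in the denominator for unsolicited events, and "subjects who did not report an event will be considered as subjects without an event".

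Neither SAP 11.2.1, 11.2.2 and 11.2.5 nor Protocol 9.5 bounds an imputed date by the vaccination date.

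**The concern.** Protocol 7.3.1 has adverse events recorded from Day 0 to Day 30, and Protocol 7.1.1 sends conditions present before the dose to medical history. An unsolicited event with a negative onset day is therefore normally an artefact of the imputation. This is a rule the SAP states, applied as written, so it is not a matter of missing detail.

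An event given a negative onset day is outside both safety windows. Because the study has a single dose, it also has no preceding dose to belong to. An event pushed past Day 30 leaves the 31-day table in the same way. In either case the subject counts as event-free unless another event of that subject is counted. Safety of the challenge dose is a secondary objective, and these percentages are among its planned outputs.

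**Working it through.** The documents give no figure for partial dates, so there is none to reproduce. The check applies the SAP rule to known onsets.

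**Inputs.** Imputation rule and onset-day definition: SAP 11.2.1. Windows of Days 0-30 and Days 0-3: SAP 6.4.1. Assumed, because the documents are silent: vaccination on each calendar date equally likely, and onset equally likely on each of Days 0-30.

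**Formula.** Imputed onset day = (15th of the recorded month) − (vaccination date). The event is counted if the result lies between 0 and 30.

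**Two single cases, day missing.**

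- Vaccination 20 September, true onset 24 September (Day 4). Imputed 15 September: 15 − 20 = Day −5. All September onsets (Days 0-10, 11 of the 31 possible days, 35%) are lost this way. October onsets go to 15 October = Day 25 and are kept.
- Vaccination 10 September, true onset 5 October (Day 25). Imputed 15 October = Day 35. All October onsets up to Day 30 (Days 21-30, 10 of 31, 32%) are lost. September onsets go to Day 5 and are kept.

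The pattern is general. Vaccination after the 15th sends same-month onsets before the dose. Vaccination in roughly the first half of a month sends following-month onsets past Day 30.

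**All vaccination dates in 2016, day missing.** There are 366 × 31 = 11,346 combinations of vaccination date and true onset day.

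| Placed by the SAP rule | Count | Share |
|---|---|---|
| Before the dose | 1,537 | 13.5% |
| Days 0-30 | 8,549 | 75.3% |
| After Day 30 | 1,260 | 11.1% |

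The 2017 calendar gives 13.5%, 75.4% and 11.1%.

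**Sensitivity to onset timing.** With early-weighted onsets (exponential weights, mean 7 days), about 32% move before the dose and 1.3% past Day 30. For true onsets on Days 0-3 alone, about 46% move before the dose and about 13% stay in Days 0-3.

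**Error in the other direction.** About 7% of day-missing onsets on Days 4-30 are pulled into Days 0-3. About 23% of day-missing onsets on Days 31-48, if recorded at a late Visit 3, are pulled into Days 0-30.

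**Scale.** Events lost = (share of events lacking a day) × (share moved out). For an assumed 1% to 20% lacking a day:

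- uniform onsets: 0.01 × 0.246 = 0.25% to 0.20 × 0.246 = 4.9% of true Day 0-30 events
- early-weighted onsets: 0.01 × 0.335 = 0.3% to 0.20 × 0.335 = 6.7%

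One subject in about 100 is 1 percentage point.

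**The case against.** The strongest reply is that the rule will seldom be used. Follow-up lasts about a month. Diary cards are collected and verified with the subject at Visits 2 and 3 (Protocol 5.6.17), eCRF omissions can be queried (10.1), and entries are checked against source (10.2). A date lacking both day and month is hardly plausible here. All analyses are descriptive. This stands, and it limits the size of the point, but it does not make the rule correct when it is used.

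Several stronger readings are tempting, and the documents do not support them:

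- *The rule generally removes post-dose events.* About three quarters of day-missing events stay in the window under the stated assumptions, and some error runs inward.
- *Early reactions to the vaccine are undercounted.* The listed local and general reactions are solicited and classified from daily recordings (Protocol 9.5), so they do not depend on a partial onset date. The 46% applies only to unsolicited, non-serious events with onset on Days 0-3 and no recorded day.
- *SAEs are lost.* They are described over the whole study period (SAP 6.4.1, Template 28).
- *The eCRF already marks such events as post-dose.* No section describes a field for this. The post-dose status follows from the recording rules in Protocol 7.1.1 and 7.3.1.
- *Each lost event costs a percentage point.* Template 26 counts subjects, so the overall rate changes only if the subject has no other counted event.

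The SAP also does not say in so many words that window membership is decided by derived onset day. That is an inference, but onset day is the only variable it defines for the purpose.

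**Conclusion.** The point holds as a minor one. For unsolicited, non-serious adverse events with a missing onset day, the stated rule can put a post-dose event before the dose or beyond Day 30. The outputs exposed are the Days 0-30 tables (Templates 26 and 31) and, for early onsets, the combined Days 0-3 table (Template 23). Because recording is confined to Days 0-30, the expected net direction in the 31-day tables is undercounting.

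The loss of about a quarter of day-missing events rests on evenly spread vaccination dates and onsets. It is about a third if onsets cluster early. The absolute effect depends on how often days are missing, which the documents do not give and which is probably low. The primary immunogenicity endpoint is not touched.

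**What to change.** In SAP 11.2.1, add a rule for adverse event onset only, and leave the existing rule for medication and vaccination history:

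- Day missing, month and year those of vaccination: use the later of the 15th and the vaccination date.
- Day missing, later month: use the earlier of the 15th and Day 30, but not before the first of the recorded month.
- Day and month missing: use the vaccination date if the year matches, or 1 January if it is the following year.
- Footnote the number of imputed onset dates in each affected table.

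Medication should stay outside the new rule because Protocol 6.7.1 records it from 30 days before the dose. About half of day-missing starts in those 30 days fall in the vaccination month and would wrongly become post-dose.

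With the month known, the same enumeration keeps 100% of true Day 0-30 onsets in the window, against 75%.

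The cost is a few sentences and a few lines of code, plus some overcounting among imputed events:

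- About 15% to 16% of day-missing Day 4-30 onsets would count in Days 0-3, against 7% now.
- About 69% of day-missing onsets on Days 31-48, if recorded, would enter Days 0-30, against 23%.
- An event with day and month both missing and the year matching becomes Day 0, so it counts in Days 0-3.

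A simpler rule (vaccination date if the month matches, otherwise the first of the month) would also keep every Day 0-30 onset, but it would put 54% of day-missing Day 4-30 onsets into Days 0-3. The bounded 15th is preferable.
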